02 JUNE 2021 VERSION 7.0

PTC THERAPEUTICS, INC. [name]

Notice of Proprietary Information: This document contains confidential information owned by or in the possession/control of PTC Therapeutics, Inc. Except as may otherwise be permitted in writing, by accepting or reviewing these materials, you agree that this information should not be disclosed to others (except where required by applicable law) and should not be used for unauthorized purposes. In the event of an actual or suspected breach of this obligation, PTC Therapeutics, Inc. should be notified promptly.

PROTOCOL IDENTIFIERS AND STUDY PERSONNEL

Project CodePTC299Therapeutic AreaVirologyPTC Therapeutics Substance IdentifierPTC299Nonproprietary NameEmvododstatIND NumberIND 149385EudraCT Number2020-001872-13

Protocol Number PTC299-VIR-015-COV19

Protocol Version 7.0

Protocol Version Date02 June 2021 **Protocol Phase**Phase 2/3

Protocol Title Evaluation of the efficacy and safety of PTC299 in

hospitalized subjects with COVID-19 (FITE19)

PTC Clinical Lead PTC Medical Monitor PTC Biostatistician PTC Study Manager

PTC THERAPEUTICS PROTOCOL APPROVAL SIGNATURES

	Date
PTC Therapeutics, Inc.	
	Date
PTC Therapeutics, Inc.	
	Date
PTC Therapeutics, Inc	

The eSignature page is located on the last page.

PRINCIPAL INVESTIGATOR AGREEMENT AND SIGNATURE

I have read the protocol document and, on behalf of my institution, agree to comply with the protocol and all applicable regulations.

Principal Investigator		Date	
Institution:			
Address:			
City:			
State/Province:			
Country:			
Phone:			
Fax:			
E-mail:			

SYNOPSIS

Study Number	PTC299-VIR-015-COV19		
Name of	Emvododstat (PTC299)		
Investigational	` ´		
Product			
Study Title	Evaluation of the efficacy and safety of PTC299 in hospitalized		
	subjects with COVID-19 (FITE19)		
Proposed Indication	Treatment of COVID-19		
Number of Study	Approximately 50		
Sites			
Phase of Trial	Phase 2/3		
Study Objectives	Primary Study Objective		
	To evaluate the clinical efficacy of PTC299 compared with placebo		
	assessed by time to respiratory improvement in adult subjects		
	hospitalized with COVID-19.		
	Secondary Study Objectives		
	To evaluate the clinical efficacy of PTC299 compared with		
	placebo, as assessed by respiratory function, immune		
	response, length of hospitalization, and mortality.		
	To evaluate the safety of PTC299 as assessed by		
	drug-related adverse events.		
Study Endpoints	Primary Endpoint		
	 Time from randomization to respiratory improvement, 		
	defined as peripheral oxygen saturation (SpO ₂)≥94% on		
	room air, sustained until discharge from the hospital or the		
	end of the study (Day 28).		
	Secondary Endpoints		
	 The proportion of subjects requiring invasive ventilation at any point during the study 		
	The proportion of subjects requiring supplemental oxygen		
	or non-invasive ventilation at any point during the study in		
	subjects who did not require supplemental oxygen at		
	baseline		
	Time from randomization to defervescence in subjects		
	presenting with fever at enrollment (temperature of		
	≥37.6°C axilla, ≥38.0°C oral, or ≥38.6°C tympanic or		
	rectal)		
	Time from randomization to respiratory rate		
	<24 breaths/minute on room air		
	Time from randomization to cough reported as mild or		
	absent (on a scale of severe, moderate, mild, absent, in		
	those with cough at enrollment rated severe or moderate)		

	,		
	 Time from randomization to dyspnea reported as mild or absent (on a scale of severe, moderate, mild, absent, in those with dyspnea at enrollment rated as severe or moderate) Attenuation of immune responses as indicated by: reduction in cytokine levels, potentially including interleukin (IL)-2, IL-6, IL-7, IL-17, granulocyte-colony stimulating factor, interferon-γ inducible protein 10, monocyte chemoattractant protein 1, macrophage inflammatory protein 1-α, and tumor necrosis factor-α reduction in levels of acute phase proteins, potentially including ferritin, C-reactive protein, D-dimer, and cardiac troponin normalization in the complete blood count changes in other laboratory parameters potentially including decreases in lactate dehydrogenase, prothrombin time, and albumin Reduction in viral load Duration of hospitalization measured in days Mortality at Day 28 Overall safety profile characterized by type, frequency, severity, timing, and relationship to study treatment of any 		
Study Population	adverse events (AEs) or laboratory abnormalities. Hospitalized adult subjects with confirmed pneumonia, diagnosed with		
Study I opulation	COVID-19, and not requiring mechanical ventilation.		
	For the purposes of enrollment of subjects into the study, "hospitalized		
	patients" will include any COVID-19 patient either admitted or under observation in the hospital for a continuous period of 24 hours or more		
	who otherwise fulfills the eligibility criteria.		
Sample Size	A total of 326 events in the study will provide more than 80% of		
	power to detect a hazard ratio of 1.38 at two-sided type I error of 0.05.		
	Approximately 380 subjects, in total, will be needed. 190 randomized to PTC299 and 190 randomized to placebo.		
	Enrollment will be halted when approximately 40 subjects (20 in each		
	arm) have been enrolled and an interim analysis of safety data will be		
	conducted when those 40 subjects have received 14 days of treatment		
	and 14 days of follow-up. Enrollment will continue if there are no safety concerns.		
Methodology/Study	This is a randomized, double-blind, placebo-controlled, multicenter		
Design	28 -day study with safety follow-up by telephone call at Day 60.		

Subjects will be randomized 1:1 to PTC299 treatment or placebo, with approximately 190 subjects in each cohort. The randomization will be stratified by age (≤62 vs >62), remdesivir use (yes vs no), and dexamethasone use (yes vs no). All subjects will also receive standard of care (SOC) defined per local written policies or guidelines. The use of steroids (except dexamethasone), sensitive CYP2D6 substrates, CYP2C inducers, IL-6 neutralizing antibodies, IL-6 receptor inhibitors, and any investigational therapy are prohibited. Following eligibility screening and enrollment, subjects will receive oral tablets containing PTC299 or matching placebo 200 mg twice daily (morning and evening) on Days 1 to 7 and 50 mg once daily (morning) on Days 8 to 14.

Approximately 40 subjects (20 in each arm) will be enrolled initially, enrollment will then halt, and an interim analysis will be performed to assess safety. No formal statistical testing will be performed at the first interim analysis. An independent data and safety monitoring board (DSMB) will review available data for the 40 subjects. Enrollment will continue if there are no safety concerns. In addition to the DSMB, an independent Hepatic Advisory Safety Committee (HAC) will also review data related to liver events.

A second interim analysis is planned to assess futility. It will be performed when 50% of respiratory improvement events have been reached, ie, 163 events have been observed (approximately 190 subjects).

The unblinded interim analyses will be conducted by an independent statistician and the results will be only shared with the closed session of the DSMB. DSMB will make the go- or no-go recommendations and the recommendations will be communicated with the study team. The study team will be kept blinded for results related to the interim analyses.

Subjects will be assessed daily while hospitalized. All subjects will undergo efficacy, safety, and laboratory assessments as summarized in Table 3. There will be a follow-up telephone call at Day 60 to assess AEs, serious AEs, and deaths.

For subjects who are discharged from the hospital prior to Day 28:

- If SpO₂ is <94%, SpO₂ measurements will be taken daily until Day 28
- Subject-reported assessments for cough and dyspnea will continue to Day 28
- No other assessments will take place except for those specified at Day 14, 28 and Day 60 in the protocol.

All subjects will undergo the assessments specified for Day 14 and Day 28, and participate in the Day 60 telephone call, even if they are discharged from the hospital prior to Day 28.

Main Inclusion Criteria

- 1. Subject (or legally authorized representative) is willing and able to provide informed consent and comply with all protocol requirements.
- 2. Agrees to the collection of nasopharyngeal swabs and venous blood and all other protocol-specified procedures.
- 3. Male or non-pregnant female adult ≥18 years of age at time of enrollment.
- 4. Hospitalized and has laboratory-confirmed infection with SARS-CoV-2.
- 5. Symptom onset was ≤14 days prior to Screening.
- 6. Has SpO₂ <94% on room air
- 7. Has at least one of respiratory rate >24 breaths/minute or cough
- 8. Lung involvement as confirmed by radiographic infiltrates observed on imaging (chest X-ray, CT scan, or an equivalent test)
- 9. Women of childbearing potential (as defined in (CTFG 2014)) must have a negative pregnancy test at screening and agree to abstinence or the use at least one of the following highly effective forms of contraception (with a failure rate of <1% per year when used consistently and correctly). Contraception or abstinence must be continued for the duration of the study following discharge from the hospital, and for up to 50 days after the last dose of study drug:
 - combined (estrogen and progestogen containing) hormonal contraception associated with inhibition of ovulation:
 - oral
 - intravaginal
 - transdermal
 - progestogen-only hormonal contraception associated with inhibition of ovulation:
 - oral
 - injectable
 - implantable
 - intrauterine device
 - intrauterine hormone-releasing system
 - vasectomized partner with confirmed azoospermia All females will be considered of childbearing potential unless they are postmenopausal (at least 12 months consecutive amenorrhea in the appropriate age group without other known or suspected cause) or have been sterilized surgically (eg, bilateral tubal ligation, hysterectomy, bilateral oophorectomy).
- 10. Men sexually active with women of childbearing potential who have not had a vasectomy must agree to use a barrier method of birth control during the study following discharge from the hospital and for up to 50 days after the last dose of study drug.

1 Paguires mechanical ventilation		
Requires mechanical ventilation Current participation in any other interventional study.		
2. Current participation in any other interventional study Alapina transaminasa/aspartata transaminasa layala >2timas tha		
3. Alanine transaminase/aspartate transaminase levels ≥3times the upper limit of normal(×ULN) or total bilirubin (Tbili) ≥2×ULN		
4. Lymphocyte count <500 lymphocytes/μL or hemoglobin		
<11.0 g/dL		
5. Stage 4 severe chronic kidney disease or requiring dialysis		
(ie, estimated glomerular filtration rate <30)		
6. Any other condition, that in the opinion of the investigator,		
may be cause to exclude the subject from the study.		
7. Use of steroids (except dexamethasone), sensitive CYP2D6		
substrates, CYP2C inducers, IL-6 neutralizing antibodies, IL-6		
receptor inhibitors, or any investigational therapy.		
8. Pregnancy or breast feeding.		
Anticipated transfer to another hospital which is not a study		
site within 72 hours.		
10. Known allergy to PTC299 or excipients		
At select sites, pharmacokinetics (PK) will be assessed after the single		
dose (Day 1) and repeated dosing Day 7 and 14. Blood samples will be		
collected on Days 1 and 7 at pre-dose (0), and 6 hours post-dose and		
on Day 14 at pre-dose (0) and 4 hours post-dose (morning dose only).		
PTC299 or matching placebo orally administered tablets at a dose of		
200 mg twice per day for Days 1 to 7 followed 50 mg orally		
administered once daily on Days 8 to 14.		
Subjects will receive treatment for 14 days then follow-up for 14 days		
to give a total study duration of 28 days, with a safety follow-up		
telephone call at Day 60.		
Subjects will be monitored closely for AEs and laboratory		
abnormalities during the study. An independent DSMB will monitor		
ongoing results to ensure subject well-being and safety as well as		
study integrity. The DSMB will make recommendations about early		
study closure or changes to study arms. Additionally, an independent		
HAC will oversee the hepatic safety of subjects in the study.		
s The primary endpoint is time from randomization to respiratory		
improvement, defined as SpO ₂ ≥94% on room air sustained until		
discharge from the hospital or the end of the study (Day 28).		
Kaplan-Meier plots of time to respiratory improvement will be		
presented. Median time to respiratory improvement will be estimated		
via the Kaplan-Meier product limit method. A two-sided 95%		
confidence interval (CI) for the median time to respiratory		
improvement will be computed for PTC299 and placebo cohorts based		
on a log-log transformed CI for the survivor function S(t). Time to		
respiratory improvement will be compared between treatment groups		
using stratified log-rank test.		

Hazard ratio and corresponding two-sided 95% CIs will be estimated using a Cox proportional hazards model, with treatment arm as a single covariate, stratified by the stratification factors.

Respiratory improvement rates at Days 7, 14, and 28 will also be estimated using Kaplan-Meier estimates on the time to respiratory improvement curve. Associated two-sided 95% CIs for each treatment group and the difference between the 2 treatment groups will be calculated using Greenwood's formula for variance derivation. Subjects will be randomized 1:1 to PTC299 or placebo (approximately 190 subjects in each cohort). The randomization will be stratified by age (≤62 vs >62), remdesivir use (yes vs no), and dexamethasone use (yes vs no).

This is a group sequential design with 2 interim analyses planned. The first interim analysis will only assess the safety and the trial will not be stopped for futility or superiority of efficacy. It will be performed after the first 40 randomized subjects have completed Day 28 or discontinued due to death, withdrew consent, or were lost-to-follow-up.

The second interim analysis is to assess futility and will be performed when 50% of respiratory improvement events have been reached, ie, 163 events have been observed (approximately 190 subjects). All subjects who have completed through Day 28, were discharged with SpO₂ >94% on room air, withdrew consent, died, were lost to follow-up, or took any COVID-19 rescue therapy during the study will be included in the interim analysis. Subjects whose primary event cannot be determined at the interim cut, ie, ongoing subjects, will not be included in the interim efficacy analysis. Subjects who died, withdrew consent, were lost to follow-up, or took any COVID-19 rescue therapy will be censored at Day 28. A stratified log-rank test will be performed and the hazard ratio (treatment vs placebo) will be compared with the futility boundary. The trial may be stopped for futility if the hazard ratio is less than 1.091. The futility boundary is based on Lan-DeMets beta spending function (non-binding option) with overall beta of 80%.

The sample size was calculated based on the primary endpoint of time to respiratory improvement. It is anticipated that the median time to respiratory improvement for the placebo group is 11 days and PTC299 treatment will decrease it to 8 days, an improvement of 3-days. Subjects will be followed for the fixed amount of time of 28 days from randomization (corresponding to the anticipated improvement rates of 0.829 and 0.912 at Day 28 for placebo and PTC299, respectively). A total of 326 events will provide more than 80% of power to detect a hazard ratio of 1.38 at two-sided type I error of 0.05. Approximately 380 subjects, in total, will be needed.

Demographic and baseline characteristics, disposition, and safety will be summarized descriptively by treatment group.

TABLE OF CONTENTS

PROTO	OCOL IDENTIFIERS AND STUDY PERSONNEL	2
PTC TE	HERAPEUTICS PROTOCOL APPROVAL SIGNATURES	3
PRINCI	IPAL INVESTIGATOR AGREEMENT AND SIGNATURE	4
SYNOP	PSIS	5
TABLE	OF CONTENTS	11
LIST O	F TABLES	14
LIST O	F FIGURES	14
LIST O	F ABBREVIATIONS AND DEFINITIONS OF TERMS	15
1.	INTRODUCTION	17
1.1.	Study Rationale	18
1.2.	Risk/Benefit Assessment	19
2.	STUDY OBJECTIVE AND ENDPOINTS	20
2.1.	Objectives	20
2.1.1.	Primary Objective	20
2.1.2.	Secondary Objectives	20
2.1.3.	Exploratory Objectives	20
2.2.	Endpoints	20
2.2.1.	Primary Endpoint	20
2.2.2.	Secondary Endpoints	20
2.2.3.	Exploratory Endpoints	21
3.	STUDY DESIGN	21
3.1.	Overall Design	21
3.2.	Justification of Dose	22

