3. STUDY DESIGN

3.1. Overall Design

This is a randomized, double-blind, placebo-controlled, multicenter 28-day study, with a safety follow-up telephone call at Day 60.

The study population is hospitalized adult subjects with confirmed pneumonia, diagnosed with COVID-19, and not requiring mechanical ventilation. For the purposes of enrollment of subjects into the study, "hospitalized patients" will include any COVID-19 patient either admitted or under observation in the hospital for a continuous period of 24 hours or more who otherwise fulfills the eligibility criteria.

Subjects will be randomized 1:1 to PTC299 treatment or placebo using a central randomization process, with approximately 190 subjects in each cohort. The randomization will be stratified by age (≤62 vs >62), remdesivir use (yes vs no), and dexamethasone use (yes vs no). All subjects will also receive standard of care (SOC), defined as the SOC per local written policies or guidelines. The use of steroids (except dexamethasone), sensitive CYP2D6 substrates, CYP2C inducers, IL-6 neutralizing antibodies, IL-6 receptor inhibitors, and any investigational therapies are prohibited.

Following eligibility screening and enrollment, subjects will receive oral tablets containing PTC299 or matching placebo 200 mg twice daily (BID) (morning and evening) on Days 1 to 7 and 50 mg once daily (QD) in the morning on Days 8 to 14.

Approximately 40 subjects (20 in each arm) will be enrolled initially, enrollment will then halt, and an interim analysis will be performed to assess safety. No formal statistical testing will be performed at the interim analysis. An independent data safety monitoring board (DSMB) and an independent HAC will review available data for the 40 subjects. Enrollment will continue if there are no safety concerns.

A second interim analysis is planned to assess futility. It will be performed when 50% of respiratory improvement events have been reached, ie, 163 events have been observed (approximately 190 subjects).

Subjects will be assessed daily while hospitalized. All subjects will undergo efficacy, safety, and laboratory assessments as summarized in Table 3. There will be a follow-up telephone call at Day 60 to assess AEs, SAEs, and deaths.

For subjects who are discharged from the hospital prior to Day 28:

- If SpO₂ is <94%, SpO₂ measurements will be taken daily until Day 28
- Subject-reported assessments for cough and dyspnea will continue to Day 28

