8.4.2. Analysis of Primary Efficacy Endpoints

The primary endpoint is time from randomization to respiratory improvement, defined as SpO₂ \geq 94% on room air sustained until discharge from the hospital or the end of the study (Day 28).

All hospitalized subjects will be followed fully to Day 28 with efficacy measurements taken daily unless they die, are lost to follow-up, or withdraw consent. For subjects who are discharged from the hospital prior to Day 28 without achieving respiratory improvement, SpO₂ measurements will be taken daily until Day 28. All measurements recorded will be used for efficacy analysis.

Subjects who achieved $SpO_2 \ge 94\%$ on room air and sustained this to Day 28 or discharge without taking any COVID-19 rescue therapy during the study will be considered as achieving the respiratory improvement event and the event date will be the first date of achieving $SpO_2 \ge 94\%$. Subjects will be censored at Day 28 if any of the following apply:

- randomized but had no follow-up
- took any COVID-19 rescue therapy during the study
- lost to follow-up prior to Day 28
- died prior to Day 28
- withdrew consent prior to Day 28
- had full follow-up without achieving sustained SpO₂ >94%.

Rescue therapy is defined as any additional medication, exclusive of SOC, used to treat a worsening of COVID-19 symptoms and recorded as rescue therapy on the eCRF.

Kaplan-Meier plots of time to respiratory improvement will be presented. Median time to respiratory improvement will be estimated via the Kaplan-Meier product limit method. A two-sided 95% confidence interval (CI) for the median time to respiratory improvement will be computed for PTC299 and placebo cohorts based on a log-log transformed CI for the survivor function S(t). Time to respiratory improvement will be compared between treatment groups using stratified log-rank test.

Hazard ratio and corresponding two-sided 95% CIs will be estimated using a Cox proportional hazards model, with treatment arm as a single covariate, stratified by the stratification factors.

Respiratory improvement rates at Days 7, 14, and 28 will also be estimated using Kaplan-Meier estimates on the time to respiratory improvement curve. Associated two-sided 95% CIs for each treatment group and the difference between the 2 treatment groups will be calculated using Greenwood's formula for variance derivation.

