##### 4.9.1. Primary Efficacy Analysis

The primary endpoint is the time from randomization to respiratory improvement (T2RI), defined as  $\text{SpO}_2 \geq 94\%$  on room air sustained until discharge from the hospital or the end of the study (Day 28).

All hospitalized subjects will be followed fully to Day 28 with efficacy measurements taken daily unless they die, are lost to follow-up, or withdraw consent. For subjects who are discharged from the hospital prior to Day 28 without achieving respiratory improvement,  $\text{SpO}_2$  measurements will be taken daily until Day 28. All measurements recorded will be used for efficacy analysis.

Subjects who achieved  $\text{SpO}_2 \geq 94\%$  and sustained to Day 28 or discharge without taking any COVID-19 rescue therapy during the study will be considered as achieving respiratory improvement event and the event date will be the first date of achieving  $\text{SpO}_2 \geq 94\%$ . For all other subjects i.e., a). randomized but had no follow-up; b). initiated any COVID-19 rescue therapy during the study, where a rescue therapy is defined as any additional medication, exclusive of SOC, used to treat worsening of COVID-19 symptoms and recorded as rescue therapy on the eCRF; c). lost follow-up prior to Day 28 d). died prior to Day 28; e). withdrawn consent prior to Day 28; f). had full follow-up without achieving sustained  $\text{SpO}_2 \geq 94\%$ , will be censored at Day 28.

Kaplan-Meier (KM) plots of time to respiratory improvement will be presented. Median time to respiratory improvement will be estimated via the Kaplan-Meier product limit method.

A two-sided 95% confidence interval (CI) for the median time to respiratory improvement will be computed for PTC299 and placebo cohorts based on a log-log transformed CI for the survivor function  $S(t)$ . Time to respiratory improvement will be compared between treatment groups using stratified log-rank test by randomization strata.

Hazard ratio and corresponding two-sided 95% CIs will be estimated using a Cox proportional hazards model, with treatment arm as a single covariate, stratified by the stratification factors.

Respiratory improvement rates at Days 7, 14, and 28 will also be estimated using KM estimates on the time to respiratory improvement curve. Associated two-sided 95% CIs for each treatment group and the difference between the 2 treatment groups will be calculated using Greenwood's formula for variance derivation.

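### The interval for the difference in improvement rate at Days 7, 14 and 28 ignores the randomization strata, so it is conservative to the extent that those factors are prognostic

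*Protocol*

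**What the plan says.** SAP 4.9.1 plans three between-arm comparisons of the primary endpoint in the full population.

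- The test compares the arms "using stratified log-rank test by randomization strata".
- The hazard ratio comes from a Cox model "with treatment arm as a single covariate, stratified by the stratification factors".
- In addition, "Respiratory improvement rates at Days 7, 14, and 28 will also be estimated using KM estimates". For these, the interval for "the difference between the 2 treatment groups will be calculated using Greenwood's formula for variance derivation".

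The protocol synopsis has the same Greenwood sentence, "Associated two-sided 95% CIs for each treatment group and the difference between the 2 treatment groups will be calculated using Greenwood's formula", and Protocol 8.4.2 repeats it. No strata, weights or pooling rule is given for the difference in any of the three places. Randomization is stratified by age (up to 62 or above), remdesivir and dexamethasone (Protocol 3.1 and 5.3, SAP 3.5). The documents announce an unstratified analysis of the primary endpoint only for subgroups (Protocol 8.4.7, SAP 4.11).

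**The concern.** With no strata mentioned, the natural reading is a pooled difference of the two Kaplan-Meier rates with the two Greenwood variances added. That makes it the one full-population comparison of the primary endpoint that leaves out the design factors, and no reason is given. Randomizing within strata keeps the arms nearly balanced on those factors, so differences between strata largely cancel from the treatment difference. The pooled variance does not know this and still charges for them.

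Precision is at stake, not validity. The medians get an interval per arm only, so these rate differences are the only between-arm estimates of the primary endpoint with an interval on an absolute scale. Readers will use them to judge the clinical size of any effect.

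**Working it through.** **Inputs.** About 190 subjects per arm (Protocol 4.1). Medians of 11 and 8 days, Day 28 rates of 0.829 and 0.912, and 326 events (Protocol 8.2, SAP 3.6). Three two-level factors, so 2 × 2 × 2 = 8 strata. Every subject without an event is censored at Day 28 (Protocol 8.4.2, SAP 4.9.1). Stratum sizes, block size and the prognostic effect of the factors are not given, so they are assumed below and shown over a range.

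**1. The plan's own figures.** Exponential rate by day t: 1 − 2^(−t/median). At Day 28 this gives 0.829 and 0.912, as stated. Power (Schoenfeld): Φ(√(326/4) × ln HR − 1.96). For HR 1.38 this is Φ(9.028 × 0.322 − 1.96) = Φ(0.948) = 82.8%; for HR 11/8 it is 82.0%. Subjects needed: 326 / 0.870 = 375, against about 380 stated. The design reproduces. No width is stated for the rate differences.

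**2. The planned interval.** With no censoring before Day 28, the Kaplan-Meier rate is the plain proportion and Greenwood's variance is p(1 − p)/n. At Day 14: √[(0.586 × 0.414 + 0.703 × 0.297)/190] = √(0.4515/190) = 0.0487, so the half-width is 1.96 × 0.0487 = 9.55 points.

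| Day | Placebo | PTC299 | Difference (points) | Half-width | 95% interval |
|---|---|---|---|---|---|
| 7 | 0.357 | 0.455 | 9.8 | 9.8 | 0.0 to 19.6 |
| 14 | 0.586 | 0.703 | 11.7 | 9.6 | 2.1 to 21.2 |
| 28 | 0.829 | 0.912 | 8.3 | 6.7 | 1.6 to 15.0 |

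**3. Where the excess comes from.** With stratum shares w_k and rates p_k, p(1 − p) = Σ w_k p_k(1 − p_k) + Σ w_k (p_k − p)². Stratified randomization removes nearly all of the second term from the true variance of the difference; the pooled formula keeps it. Take one factor splitting subjects 50/50, with rates g apart in both arms. The second term is then g²/4 per arm. At Day 14:

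- g = 0.20: √[(0.4515 − 0.02)/190] gives a half-width of 9.34, so the pooled interval is 2.3% wider.
- g = 0.40: √[(0.4515 − 0.08)/190] gives 8.67, so it is 10.2% wider.
- g = 0: no difference.

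**4. Three factors, eight equal strata** (assumed; the same hazard ratio for improvement for each factor; ranges over Days 7, 14 and 28).

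| Hazard ratio per factor | Pooled interval wider by | Its coverage (analytic) |
|---|---|---|
| 1.0 | 0% | 95.0% |
| 1.25 | 0.7–1.1% | 95.2–95.3% |
| 1.5 | 2.4–3.5% | 95.5–95.8% |
| 2.0 | 7.0–9.1% | 96.4–96.8% |

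Simulation with permuted blocks of 4 (4000 trials each) gave pooled coverage of 94.7–95.1% at 1.0, 95.2–95.8% at 1.5 and 95.9–96.4% at 2.0. The stratified interval covered 94.7–95.2%, 94.9–95.2% and 94.6–94.7%.

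**5. Unequal strata, Day 14** (assumed: dexamethasone 80%, remdesivir 30%, age above 62 45%; blocks of 4; 380 subjects; 2500 trials). Hazard ratios are for dexamethasone / remdesivir / age.

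| Hazard ratios | Pooled SE | Stratified SE | True SD | Pooled SE ÷ true SD | Coverage pooled / stratified |
|---|---|---|---|---|---|
| none | 0.0486 | 0.0486 | – | – | – |
| 0.7/0.9/0.7 | 0.0488 | 0.0480 | 0.0480 | 1.017 | – |
| 0.5/0.8/0.5 | 0.0491 | 0.0466 | 0.0469 | 1.047 | 96.2% / 95.2% |
| 0.4/0.8/0.4 | 0.0493 | 0.0454 | 0.0459 | 1.074 | 96.7% / 94.9% |

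A separate simulation of 4000 trials per setting gave pooled and stratified SEs of 0.0487 and 0.0479, 0.0488 and 0.0463, and 0.0489 and 0.0450, so stratifying narrows the interval by about 2%, 5% and 8%. Both estimators have the same true SD. The excess therefore lies in the variance formula, not in the point estimate.

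**The case against.** The case against acting is substantial, and most of it stands as a limit on the claim.

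- **Size.** If the factors are not prognostic, nothing changes. Otherwise the Day 14 half-width shrinks by 1.96 × (0.0487 − 0.0479) = 0.16 point, 1.96 × (0.0488 − 0.0463) = 0.5 point, or 1.96 × (0.0489 − 0.0450) = 0.8 point. The introduction reports more deaths among the elderly, which makes some effect of age plausible, but it gives no effect on time to improvement.
- **Validity.** Coverage is at or above nominal, and there is no bias.
- **Use.** Success rests on the time-to-improvement test (Protocol 8.1, SAP 4.9), which is already stratified. No test is attached to the rate differences.
- **Agreement with the primary test.** A reader might infer that the rate differences could contradict the primary result for no reason except the omitted strata. The documents do not support that: a rate at one day and a 28-day log-rank test measure different things. In a simulation under the same assumptions (1200 trials per setting), whether the Day 14 interval excluded zero disagreed with the stratified log-rank result in 26.8% of trials pooled and 24.0% stratified at 0.5/0.8/0.5, and in 19.1% and 18.3% at 0.7/0.9/0.7. About 90% or more of the disagreement remains after stratifying.
- **Presentation.** The planned difference equals the gap between the two printed rates. A weighted difference need not.
- **Early censoring.** Plain proportions suffice only without censoring before Day 28. The first sensitivity analysis in SAP 4.9.1.1 censors subjects without follow-up at randomization, so it needs within-stratum Kaplan-Meier rates.

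The last two points belong in the fix. None of these points makes the stratified interval worse.

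**Conclusion.** The point holds as a minor improvement in precision and consistency. The difference interval omits factors used in the randomization, the test and the hazard ratio, and it is conservative to the extent that those factors are prognostic. At Day 14 the standard error is 0% too large with non-prognostic strata, about 2% with modest effects and 5 to 8% with strong ones, with coverage up to about 96 to 97%. These figures rest on assumed stratum effects, prevalences and blocks of 4.

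A reader might infer that the intervals simply are too wide, or that they are invalid. Neither follows. The excess is zero if the factors do not predict improvement, the documents cannot settle how strongly they do, and the interval keeps at least nominal coverage. The unstratified reading itself rests on the sentence being silent about strata. The per-arm intervals, primary p-value, hazard ratio, power and success criterion are unaffected.

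**What to change.** In the synopsis, Protocol 8.4.2 and SAP 4.9.1:

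1. Keep the per-arm Kaplan-Meier rates with Greenwood intervals.
2. Compute the between-arm difference at Days 7, 14 and 28 as Σ W_k (p_1k − p_0k) / Σ W_k over the randomization strata, with Mantel-Haenszel weights W_k = n_1k n_0k / (n_1k + n_0k), and name the stratified variance (for example, the Sato variance).
3. Where there is censoring before Day 28, as in the first sensitivity analysis, use within-stratum Kaplan-Meier rates and Greenwood variances with the same weights.
4. Give strata with subjects in only one arm zero weight, or pool them by a stated rule.
5. Show the unstratified difference alongside, with a footnote that the stratified difference need not exactly equal the difference of the printed per-arm rates.

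At the least, the plan should say whether the difference is stratified. If only the SAP is changed, SAP Section 5, which now reports no change from the protocol, must record it.

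The cost is a few sentences and a few lines of code, settled before unblinding, with no new data. Sparse strata should be uncommon: with the prevalences assumed above, and independent factors, the smallest stratum expects 380 × 0.20 × 0.30 × 0.45 = about 10 subjects. Actual use of the two drugs may be more uneven, which is why the rule is needed.
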